Dynapulse: Brachial artery distensibility (BrachD) will be measured with the DynaPulsePathway (PulseMetric, Inc., San Diego California) as in our previous studies. The Dynapulse is a noninvasive portable system utilizing a standard sphygmomanometer cuff inflated in the same fashion as used to obtain blood pressure. The instrument derives BrachD using the technique of pulse waveform analysis of arterial pressure signals obtained from the sphygmomanometer. Brachial artery waveforms are uploaded to an online analysis site and analyzed for measures of vascular stiffness.

EndoPAT: Reactive hyperemia–peripheral artery tonometry (RH-PAT) by the EndoPat device (Itamar Medical Ltd., Caesarea, Israel) is a non-invasive technique that combines the traditional flow-mediated dilatation with pneumatic fingertip probes to measure arterial pulse wave amplitude and provide an objective measure of endothelial function (Reactive Hyperemia Index, RHI) and vascular stiffness (Augmentation index, AI). RH-PAT in T1D adolescents found endothelial dysfunction (lower mean RHI) (1.63 ± 0.5) when compared with children without diabetes (1.95 ± 0.3 , $p= 0.01$) compared to nondiabetic controls⁷⁶. Children with T1D underwent a second RH-PAT study 4 weeks after their initial study to determine the intrapatient variability of the technique and repeat RH-PAT scores were predicted by initial RH-PAT scores ($p= 0.0025$, mean intrapatient RHI SD=0.261, and coefficient of variation=14.8).

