Power and Sample Size: Power analysis and sample size are based on expected changes from the literature and from preliminary data for the primary outcomes for each aim. The sample size for the entire study was based on the power analysis for the subgroup analyses by age, in order to ensure adequate power to detect clinically meaningful treatment effects within each subgroup. In addition, we plan to examine the results by other characteristics (e.g. by obesity level, positive c-peptide status, etc.) in exploratory analyses which are not fully powered, but which may provide insight into heterogeneity in response to the therapy, thus guiding a future clinical trial if results of this study are positive. Desired α is set at 0.05. Since data used for this analysis are from within-subjects comparisons, repeated measures analysis will be used to compare outcome variables after each treatment (placebo, BCQR), adjusting for the randomization assignment of treatment order.

Assessment of Efficacy

The primary efficacy parameters will be change in insulin dose and CGM mean glucose on treatment versus placebo. Secondary efficacy measures will include change in post-MMT glucose and insulin AUC, and change in other CGM parameters (SD, %hyperglycemic, % hypoglycemic). Total daily basal and bolus insulin dose will be obtained at screening, and then at time zero for each medication phase. Insulin diaries will be obtained during the last week of each phase. Change in total, basal, and bolus insulin dose in units per day and total insulin in units per kg per day will be examined between medication phases to determine whether insulin requirements were lower at the end of the BCQR phase than the end of the placebo phase. Similarly, change in mean CGM glucose from the last 2 weeks of each medication phase will be examined to determine if overall mean glucose is decreased while on treatment versus placebo.

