Analysis Plan: All randomized subjects will be included in the analysis using an intention to treat analysis. The change in insulin dose, CGM-glucose and other metabolic parameters will be compared between the placebo and treatment visits in each subject using paired t-tests for univariate comparisons, and using repeated measures linear regression to adjust for covariates including age, diabetes duration, baseline HbA1c, and BMI. An interaction term will be entered into the model to examine whether the effect of treatment on either outcome differs among adults linearly by age, and if there is a significant interaction ($p<0.10$), results will be stratified by age group. We will also use interaction terms to assess whether the effect of treatment differs by BMI. We will also examine whether diabetes duration and initial HbA1c have an effect on outcomes by testing for an interaction between these continuous variables and the change in insulin dose and CGM-glucose. Change in vascular parameters will also be examined using paired t-test and repeated measures regression to determine if the treatment with BCQR affects vascular stiffness or function.

SA1: Effect on metabolic parameters (insulin dose, mean glucose and glycemic variability by CGM, postprandial glucose AUC by MMTT): While there are no published data on the effect of BCQR on insulin dose, prior data on the effect of Metformin⁸⁸ indicate that the change in daily insulin dose is normally distributed with standard error of 2.2 units (SD 7.6) and data from prior studies in adults with T1D performed at our center indicate that the change in total daily insulin dose

over 4 weeks is normally distributed with a standard deviation of 15 – 18.8 units/day. Assuming a SD of 18.8 to be conservative, we will be able to detect a true change in the daily insulin dose of matched pairs of \pm 5.9 units/day with 80% power in the overall group (n=80) and a change of 8.3 units/day within each age group (n=40). In a prior study of the efficacy of BCQR in adult patients with T2D, study participants treated with BCQR experienced a decrease in fasting plasma glucose level of 36.09 mg/dl and a decrease in post-prandial plasma glucose of 14.38 mg/dl after 12 weeks of treatment⁸⁹. In the overall study group, we will be able to detect a change in CGM-glucose of 3.1 mg/dl with 80% power in the entire study group and a change in CGM-glucose of \pm 4.4 mg/dl in each age group, assuming an SD of 10.03 mg/dl.

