SA2: Effect in sub-groups: For comparisons of change in insulin dose and CGM-glucose by group in two-sample independent comparisons assuming equal variance and using estimates of SD as in SA1, we will have 80% power to detect a difference in the effect of BCQR treatment on daily insulin dose of \pm 11.9 units/day, and a difference in change in CGM-glucose of \pm 6.4 mg/dl. For evaluation of BMI and age as continuous variables, we will have 90% power to detect a correlation coefficient of 0.307 or greater in the overall group in univariate analysis, and a slope of 0.32 for daily insulin dose or 0.37 for BMI in linear regression analysis.

SA3: Effect on vascular measures: Change in measures of vascular health (BrachD and RH-PAT RHI as primary outcomes, AI and HRV as secondary outcomes) will be compared following placebo and treatment with BCQR. In a prior study of BrachD in healthy adolescents and young adults, BrachD was normally distributed with a SD ranging from 1.04 to 1.29. We will have 80% power to detect a difference in BrachD of 0.343 mmHg⁻¹ in the entire study group, and a difference of 0.60 mmHg⁻¹ in each age group⁵⁵. A prior study in children with T1D found an intrapatient standard deviation of 0.261 for RH-PAT RHI. Assuming this intrapatient standard deviation, in the overall group we will have 80% power to detect a change in RH-PAT RHI of 0.10% between treatment and placebo visits, and 0.10% in each age subgroup (adolescents and adults).

G. Summarize Knowledge to be Gained: BCQR has shown promise in type 2 diabetes as an oral antglycemic agent that is generally well tolerated and safe and has a novel mechanism with the potential to have significant independent benefit for vascular complications. Studies so far have shown a dramatic decrease in cardiovascular events in type 2 diabetes. The mechanism and our current understanding of T1D suggest that BCQR may also benefit individuals with T1D in terms of glycemic control, insulin resistance, and vascular complication risk. This study will provide preliminary data supporting or refuting the hypothesis that BCQR is a novel oral agent that will benefit glycemic control, vascular function and stiffness, and hypoglycemia awareness in T1D.

H. References:

1. DeFronzo RA. Bromocriptine: a sympatholytic, d2-dopamine agonist for the treatment of type 2 diabetes. *Diabetes Care*. Apr 2011;34(4):789-794.

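### SA3 gives the same detectable RHI change (0.10) for 80 and for 40 completers; in an age subgroup the power for 0.10 is about 66% or 39%, not 80%

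*Combined protocol and SAP*

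**What the plan says.** Section F, Power and Sample Size, sets the error rate ("Desired α is set at 0.05") and explains where the study size comes from: "The sample size for the entire study was based on the power analysis for the subgroup analyses by age". The stated purpose is adequate power inside each age group. The group sizes appear under SA1, for insulin dose: "80% power in the overall group (n=80) and a change of 8.3 units/day within each age group (n=40".

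Under SA3, BrachD and RHI are the primary vascular outcomes. For RHI the plan carries forward an SD of 0.261 from a study of children with T1D ("Assuming this intrapatient standard deviation, in the overall group") and claims "80% power to detect a change in RH-PAT RHI of 0.10% between treatment and placebo visits, and 0.10% in each age subgroup". The EndoPAT paragraph in Methods gives the source figure as "mean intrapatient RHI SD=0.261, and coefficient of variation=14.8", from a repeat test four weeks after the first.

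For BrachD the plan says "BrachD was normally distributed with a SD ranging from 1.04 to 1.29", then "We will have 80% power to detect a difference in BrachD of 0.343" for the whole group and 0.60 for each age group.

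**The concern.** A paired detectable change is proportional to the SD of the difference divided by the square root of n. Going from 80 to 40 completers must multiply it by the square root of 2, about 1.41. The plan's insulin and CGM figures do this (8.3/5.9 = 1.41; 4.4/3.1 = 1.42). The RHI figure does not move at all, although the same SD is used for both groups.

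This matters because the plan justifies its size by power within age groups and RHI is one of the outcomes named as primary for SA3. A reader of a null RHI result in adolescents or adults would believe that the trial had 80% power for a change of 0.10 when it had clearly less.

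Two further defects make the sentence hard to use. It does not say whether 0.261 is the SD of the paired difference or of one visit. It also attaches a percent sign to a ratio: with the cited T1D mean of 1.63, 0.10% would be 0.0016.

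**Working it through.** **Inputs.** Alpha 0.05 (Power and Sample Size); two-sided is assumed, because the plan does not say and two-sided reproduces SA1. Power 80%. n = 80 and 40 completers (SA1; SA3 does not repeat them). Paired t-test (Analysis Plan). RHI SD 0.261 (SA3).

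**Formula.** Normal approximation: detectable change = (1.960 + 0.842) × SD_diff / √n. The exact version uses the noncentral t with n − 1 df.

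**Reproducing SA1.**
- Insulin, SD 18.8: 2.802 × 18.8/√80 = 5.89 and 2.802 × 18.8/√40 = 8.33. The plan has 5.9 and 8.3.
- CGM glucose, SD 10.03: 3.14 and 4.44. The plan has 3.1 and 4.4.

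So the method and the group sizes are as assumed, and SA1 enters its SD as the SD of the change.

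**RHI.** Reading A: 0.261 is the SD of the paired difference. Reading B: 0.261 is the within-patient SD of one visit, so SD_diff = √2 × 0.261 = 0.369. Values are noncentral t, with the normal approximation in brackets.

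| | n | Change detectable at 80% | Power for 0.10 |
|---|---|---|---|
| A | 80 | 0.083 (0.082) | 92% (93%) |
| A | 40 | 0.119 (0.116) | 66% (68%) |
| B | 80 | 0.117 (0.116) | 67% (68%) |
| B | 40 | 0.168 (0.164) | 39% (40%) |

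For 80% power at 0.10, 56 completers are needed on reading A and 109 on reading B, against 40 planned per age group.

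**Rounding.** The SD_diff that gives exactly 0.10 is 0.315 at n=80 and 0.220 at n=40. If 0.10 stands for anything from 0.095 to 0.105, the required ranges are 0.300–0.331 and 0.209–0.231. They do not overlap, and neither contains 0.261 or 0.369. Power at n=40 over that range is 61–70% (A) or 36–42% (B).

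**Which reading.** The word intrapatient, with a coefficient of variation of 14.8, points towards B: 0.261/0.148 = 1.76, close to a mean RHI. This is suggestive only.

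**Other settings.** One-sided testing, 90% power, other sample sizes (100/50, 60, 133/66) and an unpaired test were tried. None gives 80% power for 0.10 at both sizes.

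**BrachD.** 0.60/0.343 = 1.75, not 1.41. The implied SDs of the change are 1.08 (1.10) at n=80 and 1.32 (1.35) at n=40; the second lies slightly above the quoted 1.04–1.29. Taking that range as the SD of the change:
- 0.343 at n=80 has 83% power (SD 1.04) to 65% (SD 1.29).
- 0.60 at n=40 has 94% to 82%.

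If the range is instead a single-visit SD, with an assumed within-subject correlation of 0.3 to 0.7, the n=80 detectable change runs from 0.39 to 0.26 (SD 1.04) or from 0.48 to 0.32 (SD 1.29). So 0.343 is not refuted.

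**The case against.** The strongest reply is that 0.10 is only a detectable change. No passage calls it clinically meaningful, and the only RHI contrast in the documents, 1.63 in T1D against 1.95 in controls, is a gap of 0.32, for which 40 pairs have over 99% power on either reading. This stands: the repeated 0.10 does not show that the age groups are too small for an effect that matters. It does not make the 80% claim true.

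The 39% figure depends on a reading of 0.261 that the documents do not settle, and SA1's convention favours 66%. That is fair, and both are reported; neither is 80%.

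The percent sign might mean a relative change of 10%. With a mean of 1.63 that is 0.163, and power at n=40 would be 97% or 78%. The text does not say this, and one figure for both sample sizes would still be inconsistent.

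Rounding to one decimal would turn 0.083 and 0.119 both into 0.1, which may be how the repeat arose. The plan prints 0.10, however, and that is the value a reader will use.

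RHI is primary only for SA3. The Assessment of Efficacy paragraph limits the primary efficacy parameters to insulin dose and CGM glucose, and section A also lists EndoPAT endothelial function among the secondary outcomes. This limits the consequence without removing it.

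On BrachD, the plan quotes a range of SDs, so different values for different groups are conceivable. Still, two age groups each with an SD of about 1.32 would not pool to about 1.08.

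**Conclusion.** The concern holds. Under a single SD, 0.10 cannot be the 80%-power change at both 80 and 40 completers. For an age group, power for 0.10 is 66% if 0.261 is the SD of the paired difference and 39% if it is a per-visit SD. For the whole group the claim is conservative on the first reading (92%) and optimistic on the second (67%). These figures assume a two-sided paired t-test, 80 and 40 completers, and that 0.10 means RHI units. The normal approximation moves each power by no more than about two percentage points.

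BrachD is a smaller point: the two figures rest on unstated and different SDs, but no loss of power is shown, and 0.60 is slightly conservative when the quoted range is taken as the SD of the change. The SA1 power figures are unaffected. The sentence should be corrected; the design and the test need not change.

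**What to change.** In SA3, state the SD of the paired difference for each outcome, state that the test is two-sided, and derive both figures from that SD.

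- RHI, in RHI units without a percent sign: 0.08 (n=80) and 0.12 (n=40) if 0.261 is the SD of the paired difference; 0.12 and 0.17 if it is a per-visit SD, with the difference SD of 0.369 given as an assumption.
- BrachD, one SD for both groups: for example 0.41 and 0.59 at SD 1.29, or 0.33 and 0.47 at SD 1.04. If the quoted SD describes a single visit, using it unchanged assumes a within-subject correlation of 0.5, since SD_diff = SD × √(2(1 − r)); the text should say so.

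These are noncentral t values. The normal approximation used in SA1 gives at most 0.02 less; either will do if it is named and used throughout.

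The cost is protocol wording only, with no extra participants and no change of test. The RHI subgroup figure worsens from 0.10 to 0.12 or 0.17. The overall RHI figure becomes 0.08 (better) or 0.12 (worse). The BrachD subgroup figure barely moves at SD 1.29 (0.60 to 0.59), and the overall BrachD figure becomes 0.33 or 0.41.
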